C.8.3. Randomization to intervention and delayed intervention study arms.....	25
C.9. Overview of data collection time points.....	25
C.10. Design Considerations.....	26
C.11. Study Outcomes.....	27
C.11.a. Primary Outcome Measures.....	27
C.11.b.	27
Secondary Outcomes.....	27
C.11.c. Intermediate Outcome Measures.....	27
C.12. COVID-19 Measures.....	27
C.13. Sound Retention Efforts.....	28
C.14. Statistical Procedures:.....	28
C.14.a. Missing data.....	29
C.15. MyPEEPS Mobile RCT In-depth Interviews	30
D. Assess the feasibility of using In-home HIV tests for assessing HIV status in a sample of very YMSM by conducting follow-up testing with MyPEEPS RCT participants.....	31
REFERENCES.....	33

A. Study Purpose and Rationale

HIV infection remains a significant public health problem especially among men who have sex with men (MSM). While MSM account for only about 2% of the U.S. population¹, they are the risk group most affected by HIV, constituting 56% of persons living with HIV.² Much of the increased incidence in HIV has been reported among young MSM (YMSM) and is linked to high-risk sexual behavior.³ Disparities in HIV incidence exist among racial and ethnic minority groups and are particularly pervasive among younger MSM.⁴

At the same time, there remains a dearth of evidence-based HIV prevention interventions for diverse YMSM. To address this need, our study, in response to RFA-MD-15-012, leverages mobile technology and MyPEEPS, an existing theory-driven, multi-ethnic, group-level, evidence-based intervention for diverse YMSM.⁵ MyPEEPS (R34MH079707; PI: [name]) is a manualized curriculum developed by members of our proposed Investigative team comprised of 6 modules focusing on key intermediate social and personal factors, including knowledge (e.g., correct way to use a condom), self-efficacy for safer sex, interpersonal communication skills and behavioral skills (Appendix A). MyPEEPS was tested with 101 diverse (23% White, 39% Black, 27% Latino, 12% other) YMSM, ages 16-20 and demonstrated evidence of feasibility, acceptability, and preliminary efficacy in reducing sexual risk behaviors.⁵ As such, MyPEEPS is an ideal choice for use in this RFA as it is one of very few interventions in the literature targeted for diverse YMSM including those under 18 years of age.

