Using a participatory approach, our study will incorporate user-centered design in the translation of the MyPEEPS intervention onto a mobile platform. MyPEEPS was tested with older adolescents (16-18 year olds) and prior to the availability of non-occupational post-exposure prophylaxis (nPEP) and pre-exposure prophylaxis (PrEP); therefore, in addition to the mobile adaptation, we will update the intervention content in Aim 1. MyPEEPS Mobile will be delivered through YMSM avatars (e.g., caricature or graphic identity), on a mobile platform, whose profiles and problems are based on the formative research of the original pilot trial as well as the formative work proposed herein, and who manage their sexual health against a backdrop of personal, family-based, and relational challenges. MyPEEPS Mobile will be tested in an RCT with racially and ethnically diverse HIV-negative or unknown status YMSM aged 13-18 at four sites: Birmingham (AL), Chicago, New York City, and Seattle. Building upon our teams' extensive experience in HIV prevention, mHealth, behavioral interventions, and randomized controlled trials,¹²⁻⁴¹ *the specific aims are to:*

- 1) Ensure acceptability of MyPEEPS across diverse groups and translate the MyPEEPS intervention into a mobile-based intervention for diverse YMSM (13-18 years).
- 2) Pilot test MyPEEPS Mobile in a sample of 40 YMSM (10 at each study site).
- 3) Conduct a randomized 2-group (intervention, control) multi-site trial, with randomization to two groups at each site, to evaluate the efficacy of MyPEEPS Mobile in reducing male-male sexual risk behaviors. Our primary outcomes will be: total number of sex partners and condomless anal sex partners, frequencies for condomless anal sex acts, anal sex with and without condoms under the

influence of alcohol/drugs, nPEP and PrEP (if FDA- approved for this age group) use and self-reported HIV/STI testing.

The proposed MyPEEPS Mobile intervention is a novel and evidence-driven intervention using mobile technology to deliver HIV prevention information specifically developed for at-risk YMSM. This will be the first study to test the efficacy of a scaled-up, mobile version of an existing HIV prevention intervention originally developed for, designed by, and piloted for, a diverse group of YMSM. If efficacious, this behavioral HIV prevention mobile intervention supports widespread dissemination.

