The learning activities in each session will be adapted to mobile format, using automated responses, drop-down menus, videos and games to engage the participant in the learning activities. Consistent with the original curriculum, the mobile Much like the current group- based in-person version of MyPEEPS, these characters will present scenarios to open each session and end with a “cliff hanger” to engage participants and motivate participation in the next session. The team at LGS has worked with members of our investigative team, (Drs. [name], [name], [name]) to develop the vision for the technical components of this intervention (see Appendix A for examples of mobile adaptation approaches for activities in each module and sample screenshots). A team of software engineers and project managers at LGS will perform the software development that will be required for this study. LGS is uniquely qualified to build the technical components of the system. We anticipate that MyPEEPS Mobile will be novel, innovative, scientifically sound, scalable, translatable, and highly acceptable; thus, it is likely to have a strong public health impact.

A.3. Participant inclusion and exclusion criteria for all Aims.

To participate in any aspect of the study, participants must be: between 13 and 18 years of age; self-identify as male, non-binary, and/or genderqueer; male sex assigned at birth; understand and read English; live in the US and its territories; own or have access to a mobile device (e.g. smartphone or tablet); self-reported attraction to males and/or a history of sexual activity or interest to engage in sexual activity with other males in the next 12 months; and self-report HIV-negative or unknown status.

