We will recruit 900 participants. We will no longer be limiting our participants to these study sites and have expanded to include study participants from across the US. Using active and passive recruitment methods, the on-site project coordinator at each site will oversee and participate in recruitment efforts. The study staff hired through this project, on-site coordinator and the peer-to-peer networking efforts at each site will be used to recruit study participants. Each of our sites have previously participated in recruitment efforts for projects similar to the one proposed here and will be able to successfully recruit the study sample for this project. Our study participants will all have face-to-face contact with our study staff as a means to verify participants' identity. In order to accomplish this using an online sample, we will verify participants' identity using video conferencing (i.e. Zoom). Note: As per the RFA, we will ensure that we have an adequate number of participants in each age group (e.g., 13 year olds) to conduct valid sub-group analyses. Based on our power analysis, we will recruit at least 70 participants in each age.

C.3. Procedures for Maximizing Research Integrity.

To Maintain Blind Assessment, we will collect data through electronic surveys on tablet computers. Interviewers will remain in the room to ensure comprehension. Electronic survey completion offers several advantages: (1) It yields more accurate responses than face-to-face interviews about sensitive topics. (2) Participant can complete measures at their own pace. (3) Questions are answered privately increasing anonymity. (4) The interview structure permits skipping follow-up questions when the stem is answered negatively. (5) Computer delivery ensures uniform administration. Procedures for Maximizing Retention. We will use multiple strategies to reduce attrition.^{79,80} At baseline and follow up interviews, we will update contact information and encourage ongoing communication. We will offer multiple reminders via text, email or calls, based on participants' preference. To ensure follow-up assessments can be conducted for those who move, we will provide access to the assessment via link into a secure server, where data is encrypted at entry and no identifiers are collected.

C.4. Description of study population.

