The study population will consist of a diverse group of YMSM who live across the US. Each site will recruit an ethnically and racially diverse sample to include Blacks/African Americans, Hispanics/Latinos, American Indians/Alaska Natives, Asian Americans, Native Hawaiians and Other Pacific Islanders. We will also recruit "special populations" as described in our letters of support including: homeless youth and substance users. Race/ethnicity as well as these other special study populations (homeless or unstably housed, foster care, substance use) will be monitored throughout the study and recruitment will be adjusted and targeted with the intent of recruiting enough participants from each designated US health disparity population in sufficient numbers to conduct valid subgroup analyses.

C.5. Sample Size and Power Calculation.

We estimated the statistical power for the primary outcome of: number of condomless anal sex acts with male partners during the past 3 months (count outcome) based on the data from the MyPEEPS pilot study (R34MH079707). We estimated the statistical power for two scenarios: (1) to examine overall effect with total subjects; and (2) to conduct stratified analysis to examine the effects in some subgroups (such as by sex and/or for some racial/ethnicity subgroups). The following assumptions are used for the power estimation: (1) an 80% retention rate, at a single follow-up assessment for each

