study arm; (2) a conservative and high intra-cluster correlation (ICC) of 0.8, (3) mean number of unprotected anal sex acts with male partner partners with whom a condom was not used during the past 3 months at the baseline is 1.2,⁵ (4) all power estimations are based on $\alpha=0.05$ and 2-sided tests. Findings from our MyPEEPS pilot study indicate that the post-intervention number of condomless anal sex acts during the past 6 weeks decreased by 63%, or a relative risk (RR) of 0.37.⁵ However, the large effect was not statistically significant. Because the estimated effect size of the intervention was unreliable, instead, we use RR=0.73, one standard error over the estimated RR of 0.37, as the effect size for the examination of overall effect of intervention for total sample. This would provide a conservative estimation of minimum sample size need. For the subgroup analyses, we use the effect size of RR=0.37. To examine overall effect with total subjects, we expect that the post-intervention number of unprotected anal sex acts 27% (i.e., RR=0.73). We will have 97% power to detect such difference for the total sample size of 700. To test absolute relative difference (the equivalent margin) of <10% for the outcome with n=700. Secondly, for the stratified analyses, we will have 92% power to detect a relative risk of 0.37 in subgroups with sample size of 70. As per the RFA, we will have adequately powered comparisons that can be done separately for racial/ethnic groups, age (by year), geographic region (Northeast, South, Midwest and West), and socioeconomic status. In order to achieve this, each subgroup will need to have about 10% of the total subjects. For example, we anticipate recruiting 70 American Indians across all sites so that we will have enough power to detect a significant effect of the MyPEEPS Mobile intervention (See Planned Enrollment Table). To test whether the intervention is effective during the follow-up period, we will have 61% power to detect an absolute relative difference (the equivalent margin) of <10% or 95% power to detect an absolute relative difference of <15% for the outcome with n=70. However, we will increase target enrollment to n=900 to provide a better possibility of reaching the above indicated sample sizes for each subgroup.

C.6. Sampling Approach.

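### The 97% and 92% power figures rest on a mean of 1.2 acts from an older pilot sample and on Poisson variance, and section C.5 varies neither

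*Combined protocol and SAP*

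**What the plan says.** - **Outcome and source (C.5).** Power is for the "number of condomless anal sex acts with male partners during the past 3 months (count outcome) based on the data from the MyPEEPS pilot study". The mean is stated as one that "during the past 3 months at the baseline is 1.2" and is referenced to the pilot.
- **Other inputs (C.5).** A rate ratio (RR) of 0.73 overall and 0.37 in subgroups, two-sided 5% tests, 80% retention and an intra-cluster correlation of 0.8. The results are 97% power with 700 participants and 92% in subgroups of 70, which include each single year of age. Enrolment then rises to 900 to help fill the subgroups.
- **Pilot ages.** Section A describes the pilot as 101 "YMSM, ages 16-20 and demonstrated evidence of feasibility". Later in section A the text reads "MyPEEPS was tested with older adolescents (16-18 year olds".
- **Trial population.** A.3 admits ages 13-18 on "self-reported attraction to males and/or a history of sexual activity or interest to engage in sexual activity" with other males. C.2 adds that "we will recruit at least 70 participants in each age".
- **Distribution.** C.14 allows Poisson or negative binomial counts. No dispersion value or share of zero counts is given anywhere.

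**The concern.** For a count outcome, power depends directly on the mean and on the variance around it. The mean of 1.2 comes from a sample that, on either stated age range, contained nobody aged 13-15. The trial plans at least 3 x 70 = 210 such participants and does not require any sexual experience. A larger share with no acts would lower the mean and add variance that a Poisson model leaves out. C.5 is cautious about the effect size, but it gives no range for the mean and no allowance for overdispersion.

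The figures matter for two reasons. C.5 promises adequately powered comparisons by year of age, race/ethnicity, region and socioeconomic status, all from the same 1.2. And a null result would be read against 97%.

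The description of the 1.2 is also garbled: "mean number of unprotected anal sex acts with male partner partners with whom a condom was not used" runs acts and partners together.

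**Working it through.** **Inputs.** Mean m = 1.2, RR 0.73 (subgroups 0.37) and 80% retention, all from C.5. Allocation is not stated; 1:1 is assumed. Per arm: 700 x 0.8 / 2 = 280, and 900 x 0.8 / 2 = 360.

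**Formula.** Wald test on the log rate ratio at one follow-up: SE = sqrt(f x (1/m + 1/(m x RR)) / n), power = Phi(|ln RR| / SE - 1.96). Here f is the variance relative to Poisson, so f = 1 is pure Poisson.

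**Step 1: reproduce the plan.** With f = 1 and n = 280, SE = sqrt((0.8333 + 1.1416)/280) = 0.0840. Then 0.3147/0.0840 - 1.96 = 1.79, so power is 96.3%. Variants close to 97% also use m = 1.2 and f = 1: 98.7% with 350 per arm and no dropout, and 97.7% or 98.1% averaging two or three follow-ups at correlation 0.8. Using 0.8 as a design-effect inflation gives 79.8% or 64.2% and does not match. The subgroup 92% is recovered (91.8%) with 35 per arm and no dropout. With C.5's own 80% retention (28 per arm) it is 85.0%.

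**Step 2: what the pilot result says about variance.** C.5 reports RR 0.37 over 6 weeks, not significant, with 0.73 one standard error above it. On the log scale that standard error is ln(0.73/0.37) = 0.680, so z = 0.994/0.680 = 1.46, which agrees with non-significance. The assumptions are a two-arm comparison, equal arms, 30-50 analysed per arm (101 enrolled), and 1.2 per 3 months taken as about 0.6 per 6 weeks. The Poisson standard error is then sqrt((1/0.6 + 1/(0.6 x 0.37))/n) = sqrt(6.171/n).

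| Analysed per pilot arm | Poisson SE | Poisson z | f from SE of 0.680 | f needed for z = 1.96 |
|---|---|---|---|---|
| 30 | 0.454 | 2.19 | 2.2 | 1.25 |
| 40 | 0.393 | 2.53 | 3.0 | 1.7 |
| 50 | 0.351 | 2.83 | 3.7 | 2.1 |

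Under Poisson variance the pilot effect would have been significant in every row. Non-significance fits Poisson only with about 24 or fewer analysed per arm: 6.171 x (1.96/0.994)^2 = 24.

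**Step 3: trial power at m = 1.2 with these f values.**

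| f | N = 700 | N = 900 |
|---|---|---|
| 1.25 (non-significance, 30 per pilot arm) | 92% | 97% |
| 2.1 (non-significance, 50 per pilot arm) | 74% | 84% |
| 2.2 (standard error, 30 per pilot arm) | 71% | 81% |
| 3.7 (standard error, 50 per pilot arm) | 49% | 59% |

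The non-significance rows are upper limits on power, because f is then at least the value shown.

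**Step 4: a lower mean with Poisson variance.**

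| Mean | N = 700 | N = 900 | Subgroup of 70, no dropout |
|---|---|---|---|
| 1.2 | 96% | 99% | 92% |
| 0.9 | 90% | 96% | 83% |
| 0.6 | 76% | 85% | 66% |
| 0.4 | 58% | 69% | 49% |

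Under Poisson variance, 80% power needs a mean of at least 0.67 at 700 or 0.52 at 900.

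**The case against.** The strongest objection is that the formula above is not the planned analysis. C.14 specifies a generalized linear mixed model with person-level random effects. Table 4 gives a baseline and 3-, 6- and 9-month data in both arms, plus 12 months in the delayed arm. A participant who reports no acts throughout is a stable between-person difference, which the random intercept can absorb.

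I checked this with the Poisson information for the intervention coefficient under Table 4's coding, with a mean of 1.2 among active youth and added zeros that persist and are fully absorbed. The figures are power at 700 / 900:

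| Added zeros | Single follow-up | Table 4 model |
|---|---|---|
| 30% | 78% / 88% | 97% / 99% |
| 50% | 58% / 69% | 91% / 96% |
| 70% | 35% / 43% | 72% / 82% |

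This stands. A reader might infer that the trial's true power is 58% or 35%; the documents do not support that. The right-hand column is favourable in its turn. It takes active youth as otherwise Poisson and omits the random slopes that C.14 places on the other coefficients. The plan's 97% itself matches a single-follow-up calculation.

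Four further points stand.
- The zero share is not in the documents, and 1.2 may already include zeros.
- Recruiting homeless and substance-using youth (C.4) and using sexual networking sites (C.8) could raise the mean.
- Enrolling 900 absorbs a modest fall: 10% added zeros still gives 97% on the single-follow-up formula.
- C.14 already allows a negative binomial model, so the gap is in the sizing. A hurdle model would be a preference, not a correction.

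A reader might also infer that the 97% set the trial's size. C.5 justifies the rise to 900 by subgroup sizes.

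A null result is indeed better read from its confidence interval. That does not repair the stated power or the promise of adequately powered subgroups.

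**Conclusion.** The concern holds as one about unsupported inputs. The arithmetic behind 97% is sound. What is missing is evidence that a mean of 1.2 with Poisson variance describes 13-18 year olds admitted on attraction alone.

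The variance evidence comes from C.5 itself and does not depend on a guessed zero share. Under the stated pilot assumptions, single-follow-up power at a mean of 1.2 is 49-71% at 700 and 59-81% at 900. Using non-significance alone, it is at most about 74-92% and 84-97%. The pilot's analysed numbers, allocation and 6-week mean are assumptions, and the baseline and repeated waves may recover part of the variance too. All these figures are sensitivity values. Neither the direction nor the size of any shift in the mean can be settled from the documents.

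The subgroup claims are the more fragile. The 92% already omits the assumed dropout and falls to 66% at a mean of 0.6.

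**What to change.** 1. Restate overall and subgroup power for 900 enrolled at 80% retention, under the planned mixed model, over a stated range of baseline means (for example 0.4-1.2) and of overdispersion or zero shares. Use the negative binomial distribution that C.14 already allows.
2. Replace 1.2 with the trial's own pooled, arm-blind baseline mean, variance and zero share. C.12 shows follow-up surveys already running, so baseline data exist.
3. Interpret any null result against the restated figure and its confidence interval.
4. State that 1.2 counts acts, as C.5's definition of the outcome indicates, and remove the mixed acts/partners wording.
5. Reconcile the two pilot age ranges in section A.

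The cost is a short set of calculations and a blinded summary of data already held. No design change follows, but the stated power will probably be less favourable, most of all for the subgroups.

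### Section C.5 sets aside the pilot RR of 0.37 as unreliable, then uses it to call subgroups of 70 adequately powered; at the plan's own RR of 0.73 such a subgroup has about 23% power

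*Combined protocol and SAP*

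**What the plan says.** C.5 powers the trial on the number of condomless anal sex acts in the past 3 months. It reports a pilot RR of 0.37, notes that this was not statistically significant, and replaces it for the overall test: "Because the estimated effect size of the intervention was unreliable, instead, we use RR=0.73, one standard error over the estimated RR of 0.37". It says of that choice: "This would provide a conservative estimation of minimum sample size need". With RR 0.73 it states 97% power for 700 participants.

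The stratified scenario then uses the other value: "For the subgroup analyses, we use the effect size of RR=0.37". The result is that "we will have 92% power to detect a relative risk of 0.37 in subgroups with sample size of 70". From this C.5 concludes that "we will have adequately powered comparisons that can be done separately for racial/ethnic groups, age (by year), geographic region" and socioeconomic status. It adds that "In order to achieve this, each subgroup will need to have about 10% of the total subjects" and gives an example of recruiting "70 American Indians across all sites so that we will have enough power to detect a significant effect". Section C.2 sets a recruitment floor of 70 for each year of age and cites the power analysis as its basis.

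The last sentence of C.5 raises the target: "we will increase target enrollment to n=900 to provide a better possibility of reaching the above indicated sample sizes for each subgroup". Subgroup power at RR 0.73 appears nowhere in the document.

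**The concern.** Two effect sizes are used a few sentences apart, and the more favourable one goes where the sample is ten times smaller. The only comment C.5 makes on RR 0.37 is that it cannot be relied on. Yet the adequacy statement that follows carries no condition, and C.2 builds a recruitment floor on it.

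What is at stake is how subgroup results will be read. If the true effect in a subgroup is near RR 0.73, about three in four analyses of 70 participants would miss it. A reader who has seen 92% could then take a non-significant result in a small group, such as the American Indian participants, as a sign that the app does not work for them.

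**Working it through.** **Inputs from C.5.** Two-sided alpha 0.05; baseline mean 1.2; 80% retention; ICC 0.8; RR 0.73 with n=700 (stated power 97%); RR 0.37 with n=70 (stated power 92%).

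**Assumptions.** 1:1 allocation and Poisson variance. C.14 also allows a negative binomial distribution but gives no dispersion value. With 80% retention, 700 enrolled leaves k=280 per arm and 70 enrolled leaves k=28 per arm. Throughout, power = Φ(δ − 1.960).

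**1. Reproducing the stated figures.** C.5 gives no formula. A square-root Poisson comparison comes close to both figures if the ICC enters as the variance factor for two correlated measures, (1 + 0.8)/2 = 0.9. Two measures is an assumption.

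δ = 2(√1.2 − √(1.2·RR)) / √(2·0.9/k)

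- Overall, RR 0.73, k=280: δ = 0.319/0.0802 = 3.98, power 97.8% (stated 97%).
- Subgroup, RR 0.37, k=28: δ = 0.858/0.2535 = 3.38, power 92.3% (stated 92%).

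On this basis the 92% stands for RR 0.37.

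**2. The same subgroup at RR 0.73, without choosing a formula.** The stated 97% implies δ = 1.960 + 1.881 = 3.841 at n=700. With the same test and effect, δ shrinks with the square root of n, so the retention rate and the ICC cancel.

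- n=70: δ = 3.841/√10 = 1.215, power = Φ(−0.745) = **22.8%**.
- n needed for 80% power: 700 × (2.802/3.841)² ≈ 373.

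**3. Other routes to n=70 at RR 0.73.**

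| Route | Power |
|---|---|
| Square-root Poisson, 80% retention, ICC factor 0.9 | 24.1% |
| Rate difference, 80% retention, ICC factor 0.9 | 24.0% |
| Two-arm log-RR Wald test, 80% retention, no ICC factor | 22% |
| Same Wald test, no attrition | 26% |
| Log RR with null variance at the control mean, 80% retention | 27% |
| Back-calculated from the stated 92%, log RR, Poisson variance adjusted to RR 0.73 | 26.5% |

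The range is 22-27%. In the Wald form, SE(log RR) = √(1/(1.2k) + 1/(1.2k·RR)). At k=28 and RR 0.73 it is 0.266, so the expected 95% CI is 0.73 × exp(±1.96 × 0.266), about 0.43 to 1.23.

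**4. Larger subgroups at 900 enrolled, RR 0.73.** Even splits are assumed: 900/10 = 90, 900/6 = 150 and 900/4 = 225. The last column runs from the Wald form to the square-root form with factor 0.9, both on 80% of those numbers.

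| Subgroup | Enrolled | Scaled from 97% | Wald to square-root form |
|---|---|---|---|
| 10% subgroup | 90 | 28% | 27-30% |
| Year of age | 150 | 43% | 41-45% |
| Region | 225 | 59% | 57-62% |

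**The case against.** The strongest reply is that nothing is hidden. C.5 says openly that subgroups use RR 0.37, and it states the 92% as power for that effect. Power always depends on an assumed effect. Neither value is known to be the true subgroup effect: 0.37 is the pilot estimate and 0.73 is one standard error above it. In between, power is better. On the Wald form it is 64-74% at RR 0.50 and 44-53% at RR 0.60 (56 to 70 completers). All of this stands. It answers a charge of concealment, but it gives no reason for relying on a value just called unreliable, and it does not supply the missing condition on the adequacy claim.

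A second reply is that the planned analysis in C.14 is a mixed model over all waves. With every Table 4 wave observed and Poisson within-person variance, power at RR 0.73 is 31-38% for 56 to 70 participants. That is higher, but still far below 80%. Because C.5 does not say how the ICC enters, other models cannot be excluded.

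A third reply is that RR 0.37 could hold in one subgroup while the overall RR is 0.73. That is true. But it cannot hold in every stratum of a factor at once, and the claim covers all strata of race/ethnicity, age, region and socioeconomic status.

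Raising enrolment to 900 does not answer the point, because its stated purpose is to reach the same subgroup sizes.

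Readers might also infer more than the documents support:

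- *The 92% is a miscalculation.* It is not; it reproduces at RR 0.37.
- *Every listed subgroup has about 23% power.* That figure belongs to subgroups of about 70. In C.2, 70 is a minimum, and years of age and regions may be larger.
- *The trial as a whole is underpowered.* The overall 97% rests on RR 0.73 and is not touched by this point.

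**Conclusion.** The point holds as an inconsistency in C.5 and an overstated conclusion. At RR 0.37 the stated 92% is sound. At RR 0.73, the effect the plan itself chose as conservative, a subgroup of 70 has about 23% power, and none of the larger subgroups considered reaches 80%.

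The 22.8% rests only on the plan's stated 97% and square-root-of-n scaling. The 22-27% range adds Poisson variance and equal arms, and the figures at 900 also assume even splits. Overdispersion, which C.14 allows for, would lower the Poisson-based figures.

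The consequence is limited. C.14 sets no decision rule for subgroups, and trial conduct and type I error are unaffected. The documents promise a capability that the design has only for a very large effect, and that should be corrected before subgroup results are read.

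**What to change.** In C.5:

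1. Using the sponsor's own formula with 80% retention, report subgroup power at RR 0.73 (about 23% for n=70) beside the 92% at RR 0.37, and give the smallest effect detectable with 80% power. Name the formula and say how the ICC enters, so that these figures can be checked. They should come from that formula and not from the Wald form above, which with 80% retention gives 85.0% at RR 0.37 and so does not match the stated 92%.
2. Replace the unqualified adequacy claim, and the similar statement about 70 American Indian participants, with wording that power is adequate only for effects about as large as RR 0.37.
3. Say that subgroup results will be reported as estimates with confidence intervals, and that a null subgroup result is not evidence of no benefit.

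In C.2, add a cross-reference to this assumption where the floor of 70 per year of age is set.

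The cost is one recalculation and some rewording. The stated subgroup power becomes less favourable. The stratified analyses stay, and no extra enrolment is needed.
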